9.1.3.8. Work Productivity and Activity Impairment Questionnaire–Atopic Dermatitis

The Work Productivity and Activity Impairment Questionnaire–Atopic Dermatitis (WPAI-AD) records impairment due to AD during the past 7 days. The WPAI-AD consists of 6 items grouped into 4 domains: absenteeism (work time missed), presenteeism (impairment at work/reduced on-the-job effectiveness), work productivity loss (overall work impairment/absenteeism plus presenteeism), and activity impairment. Scores are calculated as impairment percentages (Reilly et al. 1993), with higher scores indicating greater impairment and less productivity.

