#### 6.2.4. *Derived Data*

- Age (year), derived using first dose date as the reference start date and July 1st of birth year and truncated to a whole-year (integer) age. Patients whose derived age is less than 18 will have the required minimum age of 18 at informed consent; reporting for age, age groups, and lab ranges, however will be based on their derived age.
- Age group (<65, ≥65 years old)
- Age group (<65, ≥65 to <75, ≥75 to <85, ≥85 years old)
- Body Mass Index (BMI) (kg/m^2) = Weight (kg)/((Height (cm)/100))
- BMI category (<25 kg/m^2, ≥25 to <30 kg/m^2, ≥30 kg/m^2)
- The duration of AD from diagnosis (years) = [(Date of informed consent – Date of AD diagnosis )+1]/ 365.25.
  - If year of onset is missing, duration of AD will be set as missing. Otherwise, unknown month will be taken as January, and unknown day will be taken as 01. The duration of AD will be rounded to 1 decimal place.
- Duration of AD (years) category (0 to <2 years, 2 to < 5 years, 5 to <10 years, 10 to <20 years, ≥20 years)
- Diagnosis age (years), derived using diagnosis date as the reference start date and July 1 of birth year and truncated to a whole-integer age.
- Diagnosis age group (<18, ≥18 to <50, ≥50 years old)
- Change from baseline = postbaseline measurement at Visit x – baseline measurement.
  - If a baseline value is missing, it will not be imputed and the change from baseline will not be calculated.
- Percent change from baseline at Visit x:  
 ((Post-baseline measurement at Visit x - Baseline measurement)/Baseline measurement)\*100.
  - If a baseline value is missing, it will not be imputed and percent change from baseline will not be calculated.
- Weight (kg) = weight (lbs) \* 0.454.
- Weight category (<60 kg, ≥60 to <100 kg, ≥100 kg)
- Height (cm) = height (in) \* 2.54.
- Cyclosporine inadequate efficacy (yes, no)
  - Set **yes** if the reason for discontinuation is inadequate response.
- Cyclosporine intolerance (yes, no)
  - Set **yes** if the reasons for discontinuation are: intolerance to medication or contraindication (Physician indicated cyclosporine was used and a contraindication was noted).
- Cyclosporine contraindication [ineligible] (yes, no)

- Set to **yes** if cyclosporine never used because of a contraindication
- Cyclosporine inadvisable (yes, no)
  - Set to **yes** if the following reasons were selected for either not using the medication or discontinuing the medication:

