		DLQI (0,1)	A DLQI (0,1) response is defined as a post-baseline DLQI total score of 0 or 1	Missing if the DLQI total score is missing

Measure	Description	Variable	Derivation / Comment	Imputation Approach if Missing Components
Work Productivity and Activity Impairment: Atopic Dermatitis (WPAI-AD)	The Work Productivity and Activity Impairment Questionnaire–Atopic Dermatitis (WPAI-AD) records impairment due to AD during the past 7 days. The WPAI-AD consists of 6 items grouped into 4 domains: absenteeism (work time missed), presenteeism (impairment at work/reduced on-the-job effectiveness), work productivity loss (overall work impairment/absenteeism plus presenteeism), and activity impairment. Scores are calculated as impairment percentages (Reilly et al. 1993), with higher scores indicating greater impairment and less productivity.	Employment status	Question (Q)1	Single item, missing if missing.
		Change in employment status	Employed at baseline and remained employed: Q1 = 1 at post-baseline visit and at baseline visit. Not employed at baseline and remain unemployed: Q1 = 0 at post-baseline visit and at baseline visit.	Missing if baseline or observed value is missing.
		Percentage of absenteeism	Percent work time missed due to problem: $(Q2/(Q2 + Q4))*100$	If Q2 or Q4 is missing, then missing.
		Change from baseline in absenteeism	Change from baseline: observed absenteeism – baseline absenteeism	Missing if baseline or observed value is missing.
		Percentage of presenteeism	Percent impairment (reduced productivity while at work) while working due to problem: $(Q5/10)*100$	If Q5 is missing, then missing.
		Change from baseline in presenteeism	Change from baseline: observed presenteeism – baseline absenteeism	Missing if baseline or observed value is missing.
		Overall work impairment	Percent overall work impairment (combines absenteeism and presenteeism) due to problem: $(Q2/(Q2+Q4) + [(1-Q2/(Q2+Q4))*(Q5/10)])*100$	If Q2, Q4, or Q5 is missing, then missing.

Measure	Description	Variable	Derivation / Comment	Imputation Approach if Missing Components
		Change from baseline in work impairment	Change from baseline: observed work impairment – baseline work impairment	Missing if baseline or observed value is missing.
		Percentage of impairment in activities	Percent activity impairment (performed outside of work) due to problem: $(Q6/10)*100$	If Q6 is missing, then missing.

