		Change from baseline in impairment in activities	Change from baseline: observed impairment in activities – baseline impairment in activities	Missing if baseline or observed value is missing.
European Quality of Life–5 Dimensions–5 Levels (EQ-5D-5L)	The European Quality of Life–5 Dimensions–5 Levels (EQ-5D-5L) is a standardized measure of health status that provides a simple, generic measure of health for clinical and economic appraisal. The EQ-5D-5L consists of 2 components: a descriptive system of the respondent’s health and a rating of his or her current health state using a 0 to 100 mm VAS. The descriptive system comprises the following 5 dimensions: mobility, self-care, usual activities, pain/discomfort, and anxiety/depression. Each dimension has 5 levels: no problems, slight problems, moderate problems, severe problems, and extreme problems. The respondent is asked to indicate his or her health state by ticking (or placing a cross) in the box associated with the most appropriate statement in each of the 5 dimensions. It should be noted that the numerals 1 to 5 have no arithmetic properties and should not be used as an ordinal score. The VAS records the respondent’s self-rated health on a vertical VAS where the endpoints are	
 
▪ EQ-5D mobility
 
▪ EQ-5D self-care
 
▪ EQ-5D usual activities
 
▪ EQ-5D pain/discomfort
 
▪ EQ-5D anxiety/depression
 
	Five health profile dimensions, each dimension has 5 levels: 1 = no problems 2 = slight problems 3 = moderate problems 4 = severe problems 5 = extreme problems It should be noted that the numerals 1 to 5 have no arithmetic properties and should not be used as a primary score.	Each dimension is a single item, missing if missing.
		EQ-5D VAS	Single item. Range 0 to 100. 0 represents “worst health you can imagine” 100 represents “best health you can imagine”	Single item, missing if missing.
		Change from baseline in EQ-5D VAS	Change from baseline: observed EQ-5D VAS score – baseline EQ-5D VAS score	Missing if baseline or observed value is missing.
		EQ-5D-5L UK Population-based index score (health	Derive EQ-5D-5L UK Population-based index score according to the link by using the	N/A – partial assessments cannot be saved

Measure	Description	Variable	Derivation / Comment	Imputation Approach if Missing Components

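### SAP Table JAIY.6.6 computes change in WPAI presenteeism by subtracting baseline absenteeism, so the within-arm changes are wrong if the row is programmed as written

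*SAP*

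**What the plan says.** Protocol 9.1.3.8 describes the WPAI-AD items as "grouped into 4 domains: absenteeism (work time missed), presenteeism (impairment at work/reduced on-the-job effectiveness", followed by work productivity loss and activity impairment. Mean WPAI change at Week 16 is an other-secondary endpoint without multiplicity adjustment (SAP 4.2.2). Protocol 10.3.3.2 analyses all four domains by MMRM. SAP Table JAIY.6.7 repeats this and adds ANCOVA with mLOCF as sensitivity.

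SAP Table JAIY.6.6 gives the change derivations:

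- Presenteeism: "Change from baseline: observed presenteeism – baseline absenteeism"
- Absenteeism: "Change from baseline: observed absenteeism – baseline absenteeism"
- Overall work impairment: "Change from baseline: observed work impairment – baseline work impairment"
- Activities: "Change from baseline: observed impairment in activities – baseline impairment in activities"

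The general rule in SAP 6.2.4 is "Change from baseline = postbaseline measurement at Visit x – baseline measurement".

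The missing-data rules differ by domain. For absenteeism the table says "If Q2 or Q4 is missing, then missing"; for presenteeism, "If Q5 is missing, then missing".

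**The concern.** The presenteeism row takes its baseline from another domain, so the result is not a change score for either one. It contradicts the three neighbouring rows and SAP 6.2.4. The fault is a whole word, so loss in PDF reading does not plausibly explain it; it looks like a copy from the absenteeism row.

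Three things are at stake if the row is followed:

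- The reported within-arm changes would be wrong, possibly in sign.
- Different patients would be missing. Presenteeism needs only Q5. The literal rule also needs baseline absenteeism, which is missing when Q2 or Q4 is missing and undefined when Q2 + Q4 = 0.
- It becomes unclear which baseline enters the MMRM and ANCOVA as covariate (SAP 6.2.3).

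**Working it through.** The documents give no WPAI means, SDs or power, so there is no stated figure to reproduce. The check is algebra on the derivation rows, followed by ranges under stated assumptions.

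**Size of the error.** Let P be presenteeism = (Q5/10)×100 and A be absenteeism = (Q2/(Q2+Q4))×100, both from Table JAIY.6.6.

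Literal change = P_post − A_base = (P_post − P_base) + (P_base − A_base).

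The error per patient is P_base − A_base. Example: Q2 = 2 h, Q4 = 38 h and Q5 = 5 at both visits. Then A = 2/40×100 = 5 and P = 50. The correct change is 50 − 50 = 0; the literal change is 50 − 5 = +45.

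**Misclassified improvement.** Assume Q5 takes whole numbers 0–10. There are 11×11 = 121 baseline/post pairs, of which 55 are true improvements. Under the literal rule these 55 read as follows:

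| Baseline absenteeism | Improved | No change | Worse |
|---|---|---|---|
| 0% | 0 | 10 | 45 |
| 10% | 10 | 9 | 36 |
| 20% | 19 | 8 | 28 |

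These are counts of score combinations, not of patients.

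**Arm level.** The mean shifts by mean P_base − mean A_base. For assumed means of 30–60% and 5–20%, the shift runs from 30 − 20 = +10 to 60 − 5 = +55. A true mean change of −10 becomes 0 to +45, and −20 becomes −10 to +35.

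**Between-arm contrast.** P_base − A_base is fixed before treatment, so randomisation gives it the same expectation in each arm and the contrast is unbiased in expectation. Precision depends on the covariate used:

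- Baseline absenteeism as covariate: SE ratio (literal/correct) = √[(1 − r²)/(1 − ρ²)]. Here ρ, the pre–post presenteeism correlation, is 0.3–0.7, and r, the correlation of baseline absenteeism with follow-up presenteeism, is 0–0.3. Result: 1.00–1.40.
- Baseline presenteeism as covariate: SE ratio = √[1 + s_A²(1 − q²)/(s_P²(1 − ρ²))]. Here s_P = 25, s_A = 18, q (the correlation of the two baselines) is 0.2–0.6, and absenteeism is assumed to add nothing once presenteeism is known. Result: 1.17–1.41.

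A simulation agrees (2,000 runs, 70 per arm, assumed baseline means 50 and 10, true difference −12). Estimated differences were −11.97 (SE 3.38) for the correct change, −11.91 (SE 4.44) for the literal change with baseline presenteeism as covariate, and −11.94 (SE 3.80) with baseline absenteeism. Arm means moved from −10.0 and −22.0 to +30.0 and +18.1.

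**Rows that need a symbol check.**

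- *DLQI 4-point responder.* The row prints change ≤ 4, although higher DLQI is worse and the POEM and Itch NRS rows print ≤ −4. With baseline 4–30 and post 0–30 there are 27×31 = 837 score pairs. Responders are 584 under ≤ 4 and 378 under ≤ −4. The difference is 206: 98 pairs worse by 1–4 points, 27 unchanged and 81 better by 1–3 points.
- *PBI.* The printed formula divides a weighted mean, whose weights already sum to 1, by k again. Items score 0–4, so the maximum is 4/k: 1.33 (k = 3), 1.00 (4), 0.80 (5), 0.67 (6), 0.17 (23) and 0.16 (25). A score of at least 1 is then unreachable for k > 4. The same row states 25 items, while its subscales list 6 + 5 + 4 + 5 + 3 = 23, namely items 1–23.

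**The case against.** The strongest reply is that this is a one-word slip that the SAP itself resolves. The row is labelled as change from baseline in presenteeism, SAP 6.2.4 gives the right rule, and three neighbouring rows follow it. Table JAIY.6.7 also models observed presenteeism, which does not use the faulty row, and SAP 6.2.3 adjusts for baseline. A treatment comparison free of the error is therefore already planned, and a literal error would show up as a mismatch between the observed and change displays. The size figures rest on assumed baselines, SDs and correlations.

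Most of this stands, and it limits the severity. The two SE ranges are not fully consistent with each other either: if absenteeism adds nothing given presenteeism, then r = ρq, and the first range narrows to about 1.03–1.39. But the measure-specific table is what a programmer would normally follow, and two conflicting rules cannot both stand in a prespecified plan. The per-patient error needs no assumption.

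On DLQI and PBI the reply is stronger. Each depends on one machine-read symbol, and the IGA row of Table JAIY.6.4 shows the same missing minus sign. SAP 4.3 states the DLQI criterion in words as an improvement, and the PBI text mentions no further division. Nor does the SAP say that the PBI subscales cover every item. These rows are matters to check, not established errors.

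**Conclusion.** The presenteeism row is wrong as written and should be corrected. Followed literally, it misstates every within-arm presenteeism change by baseline presenteeism minus baseline absenteeism, which is +10 to +55 points on average under the assumed baselines and enough to reverse the sign. It does not bias the randomised comparison in expectation. The cost there is precision, with an SE up to about 1.4 times as large under the assumed correlations and SDs.

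If the printed symbols are confirmed, the DLQI responder (exploratory in SAP 4.3, other secondary in Table JAIY.6.7) would count unchanged and mildly worse patients as responders. It would inflate response in both arms, with an effect on the treatment difference that depends on the share set to non-response under NRI. The exploratory PBI endpoint would be unreachable for any patient with more than 4 scored item pairs.

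The IGA sign is editorial only: Protocol 6.1 requires IGA of at least 3 at entry, so a score of 0 or 1 already means an improvement of at least 2 points. No primary or multiplicity-controlled result changes.

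**What to change.** In SAP Table JAIY.6.6, define change in presenteeism as observed presenteeism minus baseline presenteeism, missing if Q5 is missing at either visit. Confirm that the analysis program does the same and uses baseline presenteeism as the covariate.

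Then check the source PDF and, where the symbols are confirmed, correct two rows:

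- DLQI response: change ≤ −4 and baseline ≥ 4.
- PBI: Σ(PNQ_i / ΣPNQ) × PBQ_i over the scored item pairs, without division by k, for the global score and the subscales.

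Reconcile the stated 25 PBI items with the subscale lists covering items 1–23. As an editorial matter, write the IGA rule in Table JAIY.6.4 as change ≤ −2.

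The cost is a one-line SAP correction for WPAI, a PDF check, up to two further one-line corrections, clarification of the PBI item count, and one editorial sign. Data collection does not change.

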#### 4.2.2. Other Secondary Objectives

These are prespecified objectives that will not be adjusted for multiplicity.

Objectives	Endpoints
To test the hypothesis that baricitinib 2 mg QD + TCS or baricitinib 4 mg QD + TCS is superior to placebo + TCS in the treatment of patients with moderate to severe AD.	
 
• Proportion of patients achieving IGA of 0 or 1 with a <math>\geq 2</math>-point improvement at Week 4
 

To compare the efficacy of baricitinib 2 mg QD + TCS or baricitinib 4 mg QD + TCS to placebo + TCS in AD during the 16-week double-blind placebo-controlled period as measured by signs and symptoms of AD.	
 
• Proportion of patients achieving EASI50 at 16 weeks
 
• Proportion of patients achieving IGA of 0 at 16 weeks
 
• Mean change from baseline in SCORAD at 16 weeks
 
• Proportion of patients achieving SCORAD90 at 16 weeks
 
• Mean change from baseline in BSA affected at 16 weeks
 
• Proportion of patients developing skin infections requiring antibiotic treatment by Week 16
 
• Mean gram quantity of background TCS used over 16 weeks (tube weights)
 

To compare the efficacy of baricitinib 2 mg QD + TCS or baricitinib 4 mg QD + TCS to placebo + TCS in AD during the 16-week, double-blind, placebo-controlled treatment period as assessed by patient-reported outcome/QoL measures.	
 
• Percent change from baseline in Itch NRS at 2 days, 1 week, 4 weeks, and 16 weeks
 
• Mean change from baseline in Itch NRS at 2 days, 1 week, 4 weeks and 16 weeks
 
• Proportion of patients achieving a 4-point improvement from baseline in Skin Pain NRS at 16 weeks
 
• Mean change from baseline in the total score of the POEM at 16 weeks
 
• Mean change in the PGI-S-AD scores at 16 weeks
 
• Mean change from baseline in HADS at 16 weeks
 
• Mean change in the DLQI scores at 16 weeks
 
• Mean change in the WPAI scores at 16 weeks
 
• Mean change in the EQ-5D-5L scores at 16 weeks
 
• Mean number of days without use of background TCS over 16 weeks
 

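### The WPAI missing-item rule sets overall work impairment to missing when Q5 is blank, even for a patient off work all week, whose score is 100% whatever Q5 is

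*SAP*

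**What the plan says.** SAP Table JAIY.6.6 derives four WPAI-AD domain scores and gives each its own missing-item rule.

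- Absenteeism uses only Q2 and Q4: "Percent work time missed due to problem: $(Q2/(Q2 + Q4))*100".
- Presenteeism uses only Q5: "Percent impairment (reduced productivity while at work) while working due to problem". Its rule is "If Q5 is missing, then missing".
- Overall work impairment combines the two, and its rule is "If Q2, Q4, or Q5 is missing, then missing".
- Activity impairment uses only Q6.

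The questionnaire "records impairment due to AD during the past 7 days". In SAP section 4.2.2 the endpoint is listed as "Mean change in the WPAI scores at 16 weeks", among the objectives that are not adjusted for multiplicity. Table JAIY.6.7 plans MMRM for all four domains, with ANCOVA on mLOCF data as sensitivity analysis. Neither document makes an exception to the overall-impairment rule.

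**The concern.** Presenteeism cannot be observed in someone who did no work during the recall week, so Q5 is the item such a person is most likely to leave blank. If the missed time was due to atopic dermatitis, that person also has the worst possible work outcome. A rule that needs Q5 before it will score overall impairment may therefore drop values because they are at the maximum.

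At stake is the overall work impairment result. It is one of four WPAI domains in an other secondary endpoint, and WPAI-AD is one of the two instruments that protocol section 9.9 names for health economics. The primary and key secondary analyses do not use it.

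**Working it through.** The plan states no figure to reproduce here. The check applies the SAP's formula and rule to the case in question.

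**1. Roles of the items.** The documents do not print the questionnaire. From the absenteeism formula, Q2 is work time missed because of atopic dermatitis and Q4 is time worked. Q5, from 0 to 10, rates impairment while working.

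**2. Formula.** Let A = Q2/(Q2+Q4). Overall work impairment = 100 × [A + (1 − A) × Q5/10].

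**3. No hours worked, some missed (Q4=0, Q2>0).** A = Q2/Q2 = 1, so the score is 100 × [1 + 0 × Q5/10] = 100 for every Q5. Evaluating Q2 = 8, 20, 40 and 60 at each Q5 from 0 to 10 gives 100 in all 44 combinations.

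**4. Some hours worked.** With Q2 = Q4 = 20, A = 0.5 and the score runs from 50 to 100 as Q5 goes from 0 to 10. With Q2 = 39 and Q4 = 1, A = 0.975 and it runs from 97.5 to 100. Here Q5 is needed and the SAP's rule is right.

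**5. The rule applied to Q2 = 40, Q4 = 0, Q5 blank.**

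| Domain | Result under the SAP |
|---|---|
| Absenteeism | 100% |
| Presenteeism | missing |
| Overall work impairment | missing, although the formula gives 100% |
| Activity impairment | scored from Q6 |

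**6. No hours missed and none worked (Q2=Q4=0).** A = 0/0, so absenteeism and overall impairment are undefined. The table does not mention this case.

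**7. What follows in the analysis.**
- At baseline: SAP section 6.2.4 does not impute a missing baseline and calculates no change from it. The Schedule of Activities first collects WPAI-AD at Visit 2, so there is no scheduled screening value to fall back on. The patient leaves the change analysis of this domain at every visit.
- After baseline: MMRM treats the value as missing at random (section 6.4.2), although it is missing because impairment is maximal. Under mLOCF (section 6.4.3) an earlier post-baseline score is carried forward, and it cannot be worse than 100%.

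**8. Illustrative size.** The documents give no rate of full-week absence, so every input here is an assumption. If a share f of scored workers is off all week with Q5 blank and the others average m, keeping the 100% scores raises the raw arm mean by f × (100 − m).

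| f | m = 30 | m = 40 | m = 50 |
|---|---|---|---|
| 2% | 1.4 | 1.2 | 1.0 |
| 5% | 3.5 | 3.0 | 2.5 |
| 10% | 7.0 | 6.0 | 5.0 |

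For the difference between arms, take means among the other workers of 35 on placebo and 25 on baricitinib, so that the rule reports 10.0:
- f = 5% against 2%: (35 × 0.95 + 5) − (25 × 0.98 + 2) = 38.25 − 26.50 = 11.75
- f = 10% against 3%: (35 × 0.90 + 10) − (25 × 0.97 + 3) = 41.50 − 27.25 = 14.25
- f = 5% in both arms: 38.25 − 28.75 = 9.5

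The rule can therefore understate or overstate the difference.

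**The case against.** The strongest reply is that nothing shows Q5 to be blank for these patients. Neither document prints the items or a skip instruction. Protocol section 9.1.3 has the questionnaires completed on an electronic diary or tablet, and whether Q5 can be skipped there is not stated. If it is answered, the SAP scores 100% and nothing is lost. This stands, and the point has to be worded conditionally. It does not remove the point: the HADS, DLQI and EQ-5D-5L index rows of the same table say that partial assessments cannot be saved, whereas the WPAI rows carry no such statement and give item-level rules, including one for a missing Q5. The SAP therefore foresees the blank.

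A reader might infer three stronger things, none of which the documents support.

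- That the patient is deleted. Only the overall score at that visit is lost. Absenteeism and activity impairment are kept, so full absence still shows in a parallel result.
- That the rule biases the comparison toward no difference. This needs more full-week absence on placebo, for which there is no figure; with equal absence, the illustration moves the other way. Loss at baseline precedes treatment and is balanced between arms in expectation, so it costs precision and representativeness.
- That the illustrated points are the error in the planned estimate. They are shifts in raw means. The MMRM models change from baseline and draws on the patient's other visits, and the primary censoring rule already removes data after rescue or permanent discontinuation, possibly including some of the worst Week 16 cases.

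**Conclusion.** The rule is wrong as written, on an other secondary endpoint. For Q2>0 and Q4=0 it makes a score depend on an item that cannot change it, and two rows of one table treat the same patient differently. That much is certain from the SAP's formula.

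Whether scores are lost in practice rests on one assumption that the documents neither confirm nor exclude: that Q5 is blank for patients who did no work. If so, maximum scores go missing for a reason tied to their value, and neither planned analysis corrects this. If Q5 is always answered, the effect is zero. The direction of any between-arm bias is not known, and the 1.0 to 7.0 points per arm mean are illustrative only. Primary and key secondary conclusions are unaffected.

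**What to change.** In SAP Table JAIY.6.6, replace the missing-item rule for overall work impairment with the following, applied at baseline and after baseline:

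- If Q2>0 and Q4=0, overall work impairment is 100% regardless of Q5. Presenteeism stays missing if Q5 is missing.
- If Q2=Q4=0, absenteeism and overall work impairment are missing, because the formula is undefined.
- Otherwise, overall work impairment is missing if Q2, Q4 or Q5 is missing.

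The cost is one derivation line, plus the matching note in the absenteeism row for Q2=Q4=0. No new data are needed, and patients with some hours worked are scored as before.
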